12.2 Withdrawal of Subjects from the Study

A subject may be withdrawn from the study at any time if the subject, the investigator, or the Sponsor feels that it is not in the subject's best interest to continue.

All subjects are free to withdraw from participation at any time, for any reason, specified or unspecified, and without prejudice.

Reasonable attempts will be made by the investigator to provide a reason for subject withdrawals. The reason for the subject's withdrawal from the study will be specified in the subject's source documents. As noted above, subjects who discontinue study treatment early (i.e., they withdraw prior to Visit 8) should have an early discontinuation visit. Refer to Section 10 for early termination procedures. Subjects who withdraw after Visit 8 but prior to Visit 11 should be encouraged to come in for a final visit (and the procedures to be followed would include those for their next scheduled visit).

12.3 Replacement of Subjects

Subjects who withdraw from the study treatment will be replaced.
Subjects who withdraw from the study will be replaced.

13 PROTOCOL VIOLATIONS

A protocol violation occurs when the subject or investigator fails to adhere to significant protocol requirements affecting the inclusion, exclusion, subject safety and primary endpoint criteria. Protocol violations for this study include, but are not limited to, the following:

- Failure to meet inclusion/exclusion criteria
- Use of a prohibited concomitant medication

Failure to comply with Good Clinical Practice (GCP) guidelines will also result in a protocol violation. The Sponsor will determine if a protocol violation will result in withdrawal of a subject.

When a protocol violation occurs, it will be discussed with the investigator and a Protocol Violation Form detailing the violation will be generated. This form will be signed by a Sponsor representative and the Investigator. A copy of the form will be filed in the site's regulatory binder and in the Sponsor's files.

14 DATA SAFETY MONITORING

Adverse events will be monitored by the Clinical PIs (Drs. [name], [name] and [name]) in real-time. Safety and tolerability data will be summarized quarterly. Adverse event rates will be coded by body system and MedDra classification term. Adverse events will be tabulated and will include the number of patients for whom the event occurred, the rate of occurrence, and the severity and relationship to study drug. All AEs will be reviewed quarterly in the regularly scheduled quality assurance meetings of UCSF Airway Clinical Research Center, which is attended by Drs. [name], [name], [name] and [name].

15 STATISTICAL METHODS AND CONSIDERATIONS

Prior to the analysis of the final study data, a detailed Statistical Analysis Plan (SAP) will be written describing all analyses that will be performed. The SAP will contain any modifications to the analysis plan described below.

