8 STUDY TREATMENTS

8.1 Method of Assigning Subjects to Treatment Groups

There is one treatment group all subjects will be assigned to.

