8.2 Blinding

Due to the objectives of the study, the identity of test and control treatments will be known to investigators, research staff, and patients. Study treatments will not be blinded.

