15.5 Interim Analysis

No interim analysis is planned.

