16.2 Data Management Procedures

The data will be entered into a validated database. The Data Management group will be responsible for data processing, in accordance with procedural documentation. Database lock will occur once quality assurance procedures have been completed.

All procedures for the handling and analysis of data will be conducted using good computing practices meeting FDA guidelines for the handling and analysis of data for clinical trials.

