16.4 Archival of Data

The database is safeguarded against unauthorized access by established security procedures; appropriate backup copies of the database and related software files will be maintained. Databases are backed up by the database administrator in conjunction with any updates or changes to the database.

At critical junctures of the protocol (e.g., production of interim reports and final reports), data for analysis is locked and cleaned per established procedures.

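### Section 15 lets the SAP be written, and the primary analysis changed, up to the final analysis of an unblinded single-arm trial without dating or labelling the change, and the supplied SAP already departs from 15.3

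*Protocol*

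**What the plan says.** Protocol section 15 opens with the timing rule: "Prior to the analysis of the final study data, a detailed Statistical Analysis Plan (SAP) will be written". The next sentence gives the SAP authority over the protocol: "The SAP will contain any modifications to the analysis plan described below". The primary analysis is not exempted. Nothing asks for the date of a change, its reason, or a label if it came after outcomes were available. Section 16.2 says "Database lock will occur once quality assurance procedures have been completed", but does not tie the SAP to that lock.

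On design, section 8.1 says "There is one treatment group all subjects will be assigned to" and section 8.2 says "Study treatments will not be blinded"; the treatment "will be known to investigators, research staff, and patients". Section 15.5 states "No interim analysis is planned".

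On the primary analysis, protocol 15.3 has one paired t-test, on the percent change in FEV1 over the treatment period. Section 5.2 lists CT mucus score first among the secondary endpoints. The SAP instead describes a primary analysis by paired t-test of the change in CT mucus plug score and in FEV1, from baseline to end of treatment. It does not say percent, says nothing about how two endpoints share the error rate, and does not mention that it differs from 15.3.

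**The concern.** Finalising a SAP shortly before the final analysis is tolerable when treatment allocation is still masked, because the recorded data then do not reveal the effect. That protection is absent here. Every participant receives NAC and everyone knows it, so the difference between a baseline and a Day 6 measurement is one observation of the effect being tested. Spirometry is recorded daily from Day 1 to Day 6 (sections 10.5 to 10.10), and recruitment is rolling over about two years at one site. A SAP written at the latest date that section 15 permits could be written by people who have a fair idea which endpoint moved.

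There is also something to choose between. The primary objective (3.1) names both mucus plugs and lung function. Spirometry before and after bronchodilator is done at both Visit 4 and Visit 9, and neither 5.1 nor 15.3 says which FEV1 is meant. The power statement in 15.6 assumes a single test at two-sided 5%, fixed in advance. A choice among candidates after the fact, or a success rule of either endpoint, does not keep that level.

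**Working it through.** **Inputs from the documents (15.6):** SD 19, detectable change 10, two-sided alpha 0.05, n = 30, power 80%.

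**Inputs assumed:** the correlations between endpoint changes, which the documents do not give. All mean changes are zero under the null, and changes are multivariate normal.

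**Step 1. The plan's own figure.**
- Normal approximation: n = (SD × (z₀.₉₇₅ + z₀.₈₀) / change)² = (19 × (1.960 + 0.842) / 10)² = 28.3, rounded up to 29.
- Noncentral t, with noncentrality (10/19) × √30 = 2.88 on 29 df: power 79.6% at n = 30; 80% is first passed at n = 31.

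The stated 30 is reproduced. The sample size is not at fault; it is valid for one pre-fixed test.

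**Step 2. Two texts, one primary analysis.**

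| | Protocol 15.3 and 5.2 | SAP |
|---|---|---|
| Endpoint in the primary analysis | FEV1 | CT mucus score and FEV1 |
| Scale for FEV1 | percent change | change |
| Role of CT score | secondary | in the primary analysis |
| Multiplicity rule | not needed for one test | none |

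**Step 3. Error rate if any one candidate can count as the primary.** For two independent tests: 1 − 0.95² = 9.75%. Correlated cases were simulated (n = 30, paired t-tests, each at two-sided 0.05). The benefit column counts only FEV1 rising or CT score falling; its nominal value is 2.5%.

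| Candidates | Assumed correlations | Any significant, two-sided | False claim of benefit |
|---|---|---|---|
| FEV1, CT score | -0.3 | 9.5% | 4.8% |
| Pre- and post-bronchodilator FEV1, CT score | 0.8 between FEV1 states, -0.3 with CT | about 12.2% | about 6.1% |
| Same three | 0.6 between FEV1 states, 0 with CT | about 13.4% | about 6.8% |

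Separate runs differ by a few tenths of a point, so the three-candidate case is best read as 12 to 13.5%, and 6 to 7% for benefit. With two candidates a stronger correlation lowers the rate: about 9.0% at 0.5 and 7.0% at 0.9 in absolute value.

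**Step 4. What each repair achieves.**
- One FEV1 test fixed in advance: 5% two-sided, power 79.6% at n = 30, unchanged.
- Fixing 15.3 without naming the bronchodilator state: two FEV1 candidates remain, and the rate is about 8% at a correlation of 0.8 and about 9% at 0.6.
- Both endpoints primary with Bonferroni, 0.025 each: power for FEV1 at n = 30 falls to 69.7%, and 80% needs n = 37.
- Both endpoints required to be significant: no inflation, since the joint false-positive rate is below 5%. The SAP does not say that this is meant.

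**The case against.** **Was the primary chosen on the results?** A reader might infer this from the difference between the SAP and 15.3. The documents do not support it. The text supplied carries no SAP date, and since title and signature pages were removed, the absence of a date proves nothing. There is also an innocent explanation: the primary objective in 3.1 already names mucus plugs and lung function together.

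**Are outcomes reviewed as they accrue?** No section says so. Section 14 summarises safety and tolerability quarterly, and 15.5 plans no interim analysis. Section 16.4 mentions interim reports ("At critical junctures of the protocol (e.g., production of interim reports and final reports), data for analysis is locked"), but does not say what they contain. Section 9.1.14 has radiologists read the scans. The baseline mucus score must be known for eligibility, but nothing says that follow-up scores are produced before the end of the study. What stands is that the design does not prevent such knowledge, most plainly for spirometry recorded at every visit.

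**Is there no cut-off?** There is one, before the final analysis. It is too late for this design, but it exists.

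**Are there no other controls?** A primary analysis is stated in 15.3, so a departure can be seen against it, and section 15 requires modifications to appear in the SAP. Sections 17.1, 17.2 and 17.5 require IRB approval of protocol amendments and research changes. Whether these reach a change made only in the SAP is arguable, because section 15 does not name that step. None requires a post hoc label.

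**Do the error rates measure SAP timing?** Only in part. The 9.5% would follow from two primaries without a multiplicity rule even if the SAP were dated before enrolment. The rise to 12-13.5% needs the unspecified bronchodilator state. These objections stand, so the repair must cover the dual primary and the FEV1 definition as well as the date.

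**Conclusion.** The concern holds as a weakness of the rule, not as a finding about conduct. Section 15 allows the primary analysis of an unblinded single-arm trial to be set or changed when its result may be known, without a record that would let a reader tell. The supplied SAP shows that the primary analysis itself is open to this: it differs from 15.3 in endpoint and scale, with no multiplicity rule.

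The two-sided false-positive rate is about 9.5% for FEV1 or CT score, and about 12 to 13.5% with a free choice of bronchodilator state, against 5%. It would be wrong to read these as the chance of falsely claiming that NAC works. That chance is about 4.8%, and 6 to 7%, against 2.5%. All are upper bounds: they suppose that any significant candidate is always promoted, and they rest on assumed correlations. The sample size of 30 stands for a single pre-fixed test. Evidence that the SAP was approved before the first post-treatment outcomes would largely settle the timing question, but not the conflict with 15.3.

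**What to change.** In section 15, replace the timing rule with text to this effect:

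- The SAP is approved and dated before the first participant's Visit 9 outcomes are available. If that point has passed, it is frozen now.
- The FEV1 analysis in 15.3 is the single primary analysis. The same edit names the bronchodilator state, the baseline visit, the end-of-treatment visit and the scale (15.3 has percent change).
- CT mucus score is secondary, as in 5.2, and the SAP is brought into line. If both endpoints are to stay primary, the SAP states the rule: either both must succeed, or alpha is split, with the power loss in step 4 accepted or the sample size revisited.
- Any departure from 15.3 is listed with its date, labelled post hoc if made after outcomes were available, and reported beside the 15.3 result.

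With CT score secondary, the cost is wording in two documents and SAP work done earlier: no extra participants, visits or tests, and no loss of power. The downside is less freedom to make late changes without labelling them.

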15.1 Data Sets Analyzed

All eligible patients who receive at least one dose of the study drug (the Safety Population) will be included in the safety analysis.

15.2 Demographic and Baseline Characteristics

The following demographic variables at screening will be summarized: race, gender, age, height, weight, baseline FEV1, and baseline post-bronchodilator FEV1.

15.3 Analysis of Primary Endpoint

The primary analysis is a paired t-test analysis of the % change in FEV1 from the start to the end of the one week treatment period with four times daily NAC (Mucomyst-20). The secondary analysis will be to determine how the change in FEV1 relates to the change in CT mucus score.

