4 STUDY DESIGN

4.1 Study Overview

This is a single center, single arm, non-randomized trial in 30 patients with asthma who demonstrate mucus plugging on a screening CT lung scan. Following outpatient screening studies, each subject will be admitted for 6 days/5 nights and receive NAC mixed with albuterol by nebulizer four times daily. After the active treatment phase, the subjects will be followed for 3 additional months as outpatient to track changes in CT lung scans in the off treatment period. Total duration of participation will be four months. Total duration of the study is expected to be 2 years.

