5 CRITERIA FOR EVALUATION

5.1 Primary Efficacy Endpoint

FEV1 will be the primary endpoint because it is the most robust measure of airflow obstruction in asthma. We will compare post-treatment FEV1 to pre-treatment baseline values.

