15.6 Sample Size and Randomization

We propose a sample size of 30, which will provide us with the power to examine the effect of NAC in a subgroup of individuals with asthma who have CT evidence of intraluminal mucus and to identify the CT mucus score that performs best as a biomarker of treatment response to NAC. Participants will be enrolled if their CT mucus scores are ≥ 5.0 . To calculate sample size for the one-week treatment period study, we used FEV1 measures from 219 adults with asthma published in Corren et al. NEJM, 2011¹. The authors found that the standard deviation for the change in FEV1 in liters from day 1 to day 7 was 19%. Using a standard deviation of 19 and a two-sided alpha of 0.05, we calculate a sample size of 30 to have 80% power to detect a change in FEV1 of 10% (a reasonable effect size because early studies of Pulmozyme in CF reported a 10% increase in FEV1 at day 3 of treatment).⁷

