[name], MSC
Clinical Research Protocol
INPATIENT CLINICAL TRIAL OF NAC IN ASTHMA (ICON)

Protocol Number:	17-24231
NCT Number	NCT03581084
Investigational Product:	n-acetylcysteine
Development Phase:	4
Sponsor:	[name], MSc [name]
Funding Organization:	NIH
Principal Investigator:	Name: [name], MSc [contact] [contact] E-mail: [contact]

STATISTICAL ANALYSIS PLAN

Our overarching method (experimental approach) is to test the efficacy of inhaled NAC delivered for 5 days to asthma patients who have baseline evidence of mucus plugs on CT lung scans. We will assess if the NAC treatment causes the mucus plugs to go away by the end of the treatment period and we will assess for reappearance of mucus plugs at 6 weeks and 3 months time. We will also examine whether any NAC associated decrease in mucus plugs is associated with improvement in FEV1. A primary analysis will be paired T-test analysis of the change in CT mucus plug score and in FEV1 from baseline to end treatment. Secondary analyses will look at the 6 week and 3 month time points.

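### The primary FEV1 test uses percent change against zero with no control arm, which can bias it modestly towards NAC; the SAP names no scale, so scale and baseline need fixing

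*Protocol*

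**What the plan says.** - **Primary test.** Protocol 15.3, repeated in the synopsis, specifies "a paired t-test analysis of the % change in FEV1 from the start to the end" of the treatment period.
- **Sample size.** Protocol 15.6 works on a percent scale: "Using a standard deviation of 19 and a two-sided alpha of 0.05", and then "we calculate a sample size of 30 to have 80% power to detect a change in FEV1 of 10" percent. The source SD is described oddly: "the standard deviation for the change in FEV1 in liters from day 1 to day 7 was 19", followed by a percent sign.
- **Design.** Protocol 4.1: "This is a single center, single arm, non-randomized trial in 30 patients with asthma". Each patient is compared only with his or her own baseline.
- **Endpoint.** Protocol 5.1 gives no scale: "We will compare post-treatment FEV1 to pre-treatment baseline values". Appendix 1 has spirometry at Visits 1, 2, 3 and 4, and no section says which of these form the baseline.
- **SAP.** "A primary analysis will be paired T-test analysis of the change in CT mucus plug score and in FEV1 from baseline to end treatment". There is no percent sign, no litres and no log. Protocol 15 says of the SAP: "The SAP will contain any modifications to the analysis plan described below".

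Neither document mentions a log or ratio scale, or the behaviour of a mean percent change when there is no effect.

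**The concern.** A percent change is the ratio of end to baseline FEV1, minus one. If baseline FEV1 carries measurement error or day-to-day variation, low readings inflate the ratio by more than high readings deflate it. The average ratio is then above one even when baseline and end values vary about the same level. The distribution is also right-skewed.

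In a randomised trial both arms would carry this bias and it would largely cancel. Here the mean is tested against zero, so the bias goes straight into the primary result and favours the drug. At stake are the split of the 5% error between the two tails and the size of the reported gain.

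**Working it through.** **1. The plan's own figure.** Inputs from Protocol 15.6: SD 19, change 10, two-sided alpha 0.05, power 80%.

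n = (19 × (1.960 + 0.842) / 10)² = 28.3, so 29 by the normal formula. With the noncentral t the minimum is 31, and power at n = 30 is 79.6%. The stated 30 and 80% are reproduced within rounding.

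**2. Mean percent change under no effect.** Assumption: all of the 19% is noise, equal and exchangeable at baseline and end. Then ln(end/baseline) is symmetric about zero with SD σ. For a lognormal ratio:

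- SD of percent change = √[(exp(σ²) − 1) exp(σ²)]. Setting this to 0.19 gives σ = 0.185.
- Null mean = exp(σ²/2) − 1 = exp(0.0343/2) − 1 = +1.73 points.
- Taking 0.19 as the log SD gives +1.82 points. The shortcut 0.5 × 0.19² gives +1.8.

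At n = 30 and SD 19 the observed mean needed for significance is 2.045 × 19/√30 = 7.1 points, so 1.73 is about a quarter of it.

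**3. Error rates.** Simulated trials of n = 30, no true change, two-sided 5% t-test:

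| Scale and assumption | Null mean (points) | For NAC | Against NAC | Total |
|---|---|---|---|---|
| Percent change, all noise, equal split | +1.7 | 5.5% | 1.1% | 6.6% |
| ln ratio, same assumption | 0 | 2.5% | 2.5% | 5.0% |
| Litres, same assumption | 0 | 2.5% | 2.5% | 4.9% |

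Under the same assumption a true 10% gain is estimated on the percent scale as about 11.9%.

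**4. Sensitivity.** The documents give no error model, so the range matters.

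| Change in assumption (percent-change scale) | Null mean (points) | For NAC |
|---|---|---|
| 75% of variance is noise, the rest real variation in response averaging zero | +1.3 | 4.2-4.3% |
| 50% of variance is noise | +0.9 | 3.2-3.5% |
| Heavy-tailed or mixed-variance log ratios, similar SD | +1.7 | 4.3-4.5% |
| SD of percent change 15% | +1.1 | 4.7% |
| SD of percent change 10% | +0.5 | 3.9% |
| Baseline carries 25% of the error variance | +0.9 | 3.8% |
| Baseline carries no error | 0 | 2.5% |
| Baseline carries 75% of the error variance | +2.8 | 7.7% |

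The 25% row is what averaging three pre-treatment visits with independent errors would give: (1/3) / (1/3 + 1) = 25%.

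**5. Power on the log scale.** For ln(1.10) = 0.0953 at n = 30, power is 77.9% at log SD 0.185 and 75.7% at 0.19, so about 76-78%.

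**The case against.** **The SAP may mean litres.** It omits the percent sign, and the protocol lets the SAP modify the analysis. If litres are meant, this bias does not arise. That stands as a limit: a reader might infer that the bias is certain to enter the reported analysis, and the documents do not settle that. But the SAP announces no change of scale, and Protocol 15.3 and the synopsis still say percent, so the ambiguity itself needs resolving.

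**The doubling is not the general case.** A reader might infer that the trial's error rate doubles from 5% to 10%. It does not. Only the tail in favour of NAC roughly doubles, and total error reaches about 6.6%. Even that needs all of the 19% to be noise, split equally. It is the upper case for equal noise; real variation in response or an averaged baseline makes it smaller. Only a baseline noisier than the end value would make it larger.

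**A single noisy baseline is not stated.** The reference to the start of treatment suggests Day 1, but four pre-treatment spirometry visits exist and the denominator is undefined. This stands.

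**The 19% is uncertain.** It comes from another trial and is described as litres but given as a percent. The calculation uses it as the plan does, as the SD of the percent change.

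**The log scale is not uniquely correct.** This also stands. It is unbiased only if noise is symmetric on that scale. If errors average out on the arithmetic scale and the baseline carries 25% of their variance, the log mean under no effect is −(0.75 − 0.25) × 0.0343/2, about −0.9 points. The favourable tail is then 1.3-1.6% and the unfavourable 3.7-4.3%. Litres held 2.1-2.9% per tail in that setting.

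**The bias is small** beside a 10-point target in an openly uncontrolled study. True, and it limits the severity.

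**Conclusion.** The concern holds as a should-fix. As Protocol 15.3 is written, the primary test can lean towards NAC. With the plan's SD of 19% and all of it equal noise, the bias is about +1.7 to +1.8 points, with rejections of about 5.5% for NAC and 1.1% against. Under milder assumptions the favourable tail falls to about 3-4%, and it is nominal if the baseline is free of error or the SAP's change is in litres.

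What is firm is the direction of the bias on the percent scale whenever the baseline contains error, the lack of a control arm to remove it, and the failure of the two documents to name one scale and one baseline. The exact size is conditional on an error model that the documents do not give.

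**What to change.** In Protocol 15.3, the synopsis and the SAP, name one scale for the primary FEV1 test and the pre-treatment visit or visits that form the baseline.

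Preferred: a paired t-test on ln(FEV1), post-treatment minus pre-treatment, reported as exp(mean difference) − 1 with a 95% CI. Use the same scale for the 6-week and 3-month FEV1 contrasts. A paired t-test in litres is an acceptable alternative and also holds about 2.5% per tail.

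If the log scale is chosen, restate power in 15.6 as about 76-78% for a 10% gain (79.6% on the percent scale as planned). In either case, state whether the 19% is a percent or a litre figure.

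Cost: wording only, with no new patients, visits or measurements. The stated power drops by about 2 to 4 points, and the log scale estimates a geometric rather than an arithmetic mean change.

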| DURATION OF SUBJECT PARTICIPATION AND DURATION OF STUDY | Subjects will be in the study for up to 91 days. Screening: up to 14 days Treatment: 5 days (subjects to be admitted to the hospital) Follow-up: 3 months The total duration of the study is expected to be 24 months. Subject recruitment will happen on a rolling basis. |
| CONCOMITANT MEDICATIONS | Prohibited: 
 • thiols and thiol derivatives • activated charcoal • inhaled insulin |
| EFFICACY EVALUATIONS | |
| PRIMARY ENDPOINT | The primary endpoint is the FEV1. Post-treatment FEV1 will be compared to pre-treatment baseline values. |
| SECONDARY ENDPOINTS | Secondary efficacy endpoints include: 
 • CT mucus score • FVC • PEF (AM and PM) • Air trapping (RV/TLC ratio) • FeNO • Blood eosinophils |
| OTHER EVALUATIONS | |
| SAFETY EVALUATIONS | Incidence of adverse events |
| PLANNED INTERIM ANALYSES | No interim analysis is planned. |
| STATISTICS Primary Analysis Plan | The primary analysis is a paired t-test analysis of the % change in FEV1 from the start to the end of the one week treatment period with four times daily NAC (Mucomyst-20). The secondary analysis will be to determine how the change in FEV1 relates to the change in CT mucus score. |
| Rationale for Number of Subjects | We propose a sample size of 30, which will provide us with the power to examine the effect of NAC in a subgroup of individuals with asthma who have CT evidence of intraluminal mucus and to identify the CT mucus score that performs best as a biomarker of treatment response to NAC. Participants will be enrolled if their CT mucus scores are ≥ 5.0 . To calculate sample size for the one-week treatment period study, we used FEV1 measures from 219 adults with asthma published in Corren et al. NEJM, 2011 ¹ . The authors found that the standard deviation for the change in FEV1 in liters from day 1 to day |

| | |
|--|---|
| | 
7 was 19%. Using a standard deviation of 19 and a two-sided alpha of 0.05, we calculate a sample size of 30 to have 80% power to detect a change in FEV1 of 10% (a reasonable effect size because early studies of Pulmozyme in CF reported a 10% increase in FEV1 at day 3 of treatment).⁷
 |
|--|---|

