10.5 Visit 4 (Day 1)

1. Record changes to concomitant medications.
2. Perform and record vital signs.
3. Perform and record oximetry.
4. Perform and record fractional exhaled nitric oxide (FeNO) measurement.
5. Perform and record spirometry.
6. Perform and record 3 peak flow AM measurements before first treatment of the day.
7. Perform and record post-bronchodilator reversibility.
8. Admit patient to medical-surgical floor.
9. Administer study drug treatment three times over the course of the day, spaced every 4-6 hours. Peak flow measurements should be taken before and after each treatment.
10. Perform and record 3 peak flow PM measurements after all treatments have been completed.

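### Is the primary FEV1 variable left open between percent and litres, and between pre- and post-bronchodilator values?

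*Protocol*

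**What the plan says.** **Scale.** The synopsis and Protocol 15.3 specify a "paired t-test analysis of the % change in FEV1 from the start to the end of the one week treatment period". Protocol 5.1 gives no scale: "We will compare post-treatment FEV1 to pre-treatment baseline values". The SAP lists a "paired T-test analysis of the change in CT mucus plug score and in FEV1 from baseline to end treatment", again with no scale. Protocol 15.6 (repeated in the synopsis) takes from an external asthma trial a "standard deviation for the change in FEV1 in liters from day 1 to day 7 was 19", with a percent sign directly after the 19. It then sizes the trial for a 10% change.

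**Bronchodilator state.** None of these passages names one. Spirometry is recorded at Visit 4 (Day 1) and Visit 9 (Day 6), and so is the post-bronchodilator test (10.5: "Perform and record post-bronchodilator reversibility"; 10.10 has the same item). Section 15.2 treats the two as separate variables: "demographic variables at screening will be summarized: race, gender, age, height, weight, baseline FEV1, and baseline post-bronchodilator FEV1".

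**Role of the SAP.** Section 15 says that "a detailed Statistical Analysis Plan (SAP) will be written describing all analyses that will be performed", and adds that the SAP will hold any modifications to the protocol's analysis plan. The SAP is one paragraph and announces none on this point.

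**The concern.** Read quickly, the documents offer percent change (15.3), litres (15.6) and plain change (SAP), each for pre- or post-bronchodilator FEV1. Two scales and two states would make four candidate primary results. With no control arm and no blinding, prespecification is the main protection against choosing the most favourable one.

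The choices are not empty. Percent change divides by a baseline measured with error, so it drifts upward when nothing has changed; change in litres does not. The two bronchodilator states could also respond differently. Each study dose contains albuterol, the medication holds in Table 2 may be shortened or waived by a clinician, and the post-bronchodilator test allows four to eight puffs. The stake would be a primary result that depends on a decision made after the data are seen.

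**Working it through.** **1. Does the sample size identify the scale?** Inputs from 15.6: SD 19, difference 10, two-sided alpha 0.05, power 80%, one group measured twice.

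- Normal approximation: N = (19 × (1.960 + 0.8416) / 10)² = (19 × 2.8016 / 10)² = 28.3, so 29.
- Exact t-test: N = 31. At N = 30 the power is 79.6%.

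The stated 30 lies between these, so it reproduces with both inputs as percentages. Now read the SD as 0.19 L, with an effect of 10% of an assumed mean baseline:

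| Assumed baseline | Effect | N for 80% power (exact t) |
|---|---|---|
| 1.5 L | 0.15 L | 15 |
| 2.0 L | 0.20 L | 10 |
| 2.5 L | 0.25 L | 7 |

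None is near 30. The trial was sized in percent, and the mention of litres is a mislabelled unit.

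**2. Does the SAP contradict 15.3 on scale?** Side by side, 15.3 says percent change and the SAP says change. The second is less specific but not incompatible. In its own next sentence 15.3 drops the percent sign when it relates the same FEV1 quantity to the change in CT mucus score. Section 15 makes the SAP the place for modifications, and the SAP declares none here, so 15.3 stands. No passage proposes a litres analysis. Percent of predicted is not a natural reading either, because the eligibility criteria say predicted when they mean it.

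**3. Is percent change the wrong scale?** Suppose a share w of the SD² is measurement noise, split equally over the two visits. The noise variance per visit is then w × 0.19² / 2. To first order the upward drift in percent change equals that variance:

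- w = 0: no drift
- w = 0.5: 0.5 × 0.0361 / 2 = 0.0090, or 0.9 points
- w = 1: 0.0361 / 2 = 0.018, or 1.8 points (1.9 by simulation)

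The documents give no value for w. The drift belongs to the protocol's chosen scale; it does not show that the scale is undefined. Litres would avoid it at some cost: with w = 0 and a baseline coefficient of variation of 20% to 40% (assumed), power for the same 10% gain is 78% to 74%, against about 80% for percent.

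**4. What is left: the bronchodilator state.** Compare two paired t-tests of percent change, each with n = 30, SD 19 and the same true effect, correlated within patient (assumed; the documents give no correlation). Only significant gains are counted:

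| Pre/post correlation | Verdicts differ, true 10% gain | Either shows a gain, no effect |
|---|---|---|
| 0.5 | 23% | 4.5% |
| 0.7 | 18% | 4.2% |
| 0.9 | 10% | 3.7% |

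For comparison, two independent tests at 79.6% power would differ in 2 × 0.796 × 0.204 = 32.5% of trials. So the 10% to 23% mostly reflects moderate power and imperfect correlation. The last column, against a nominal 2.5%, is reached only if someone computes both and reports the better one.

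**5. How would an analyst fill the gap?** Section 15.2 uses FEV1 alone for one variable and adds a qualifier for the post-bronchodilator one. Sections 9.1.9 and 9.1.10 and Appendix 1 separate spirometry from the post-bronchodilator test in the same way. The Table 2 holds apply at Visits 4 and 9. This points to pre-bronchodilator FEV1 from Visit 4 (Day 1, before the first dose) to Visit 9 (Day 6). The one-week wording in 15.3, against a five-day treatment, does not alter which visits bracket the treatment.

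**The case for a change.** The strongest case for acting is that the SAP was promised as a detailed document, may modify the protocol, and still does not name the bronchodilator state. Plain FEV1 is not conclusive: the inclusion criteria do write pre-bronchodilator when they mean it, and the rationale in 1.1 and Figure 3 rests on post-albuterol FEV1. A few words would close the matter at no cost in visits or patients.

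The observation stands: the state is unwritten, and a reader could defend either choice. What does not follow is that the plan is wrong. Either state is an acceptable primary variable, and both are collected at both visits. Writing the choice down would record a decision without improving the method.

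The larger figures that a four-way reading produces also fall away. With a true gain, the four readings would fail to agree in 15% to 35% of trials, but that counts a litres endpoint no passage proposes. A false-gain rate of 4.2% to 5.8% for the best of four is not an upper limit either, because it assumes no measurement noise. It would be higher with noise, but it still describes a choice the documents do not offer.

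**Conclusion.** No change to the plan follows. On scale there is no conflict: percent change is stated twice, the SAP's shorter wording is compatible with it, and litres is a unit slip that leaves N = 30 intact (power 79.6%). Switching to litres would remove a possible drift of 0 to 1.9 points, depending on an unknown noise share, but would lower power to about 74% to 78% under the noise-free assumption. That is a trade-off, and it does not correct an error.

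On bronchodilator state the omission is genuine but small. The more natural reading is pre-bronchodilator FEV1, Day 1 to Day 6, and the post-bronchodilator result is available beside it. The two could give different verdicts in roughly 10% to 23% of trials with a true 10% gain, assuming correlation 0.9 to 0.5 and equal SD and effect in both states. Choosing the better of the two would raise the false-gain rate from 2.5% to about 3.7% to 4.5%, and nothing in the documents calls for that choice. This is missing detail of the kind analysts settle when they define the analysis variable.
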